9.3.2.2 Secondary outcomes

- Kidney disease progression (defined as incidence of ESKD, a sustained decline in eGFR to <10 mL/min/1.73m², renal death, or a sustained decline of ≥40% in eGFR from baseline)
- Cardiovascular death
- All cause death
- Hospitalization for heart failure
- Change from baseline in eGFR to the last observation on treatment

ESKD is defined as the initiation of maintenance dialysis or receipt of a kidney transplant

9.3.3 Covariates

The following variables based on physician's report will be considered important baseline (the start of the treatment with JARDIANCE[®] Tablets) characteristics and potential risk factors for the outcomes of interest.

Demographics:

Hospitalization/outpatients, gender, year of birth, indication, diagnosed date of CKD, cause of kidney disease (diabetic kidney disease, hypertensive nephrosclerosis, glomerulonephritis [the type of nephritis: IgA nephropathy, focal segmental gomerulosclerosis, etc], multiple pustular kidney, transplanted kidney, other), pregnancy status, height, body weight, body mass index (derived), waist circumferences, smoking histoy, alcohol habit, eGFR at baseline, eGFR at 12 months and 6 months before the baseline (derived)

Medical history / Concomitant disease:

T1DM/T2DM, hypertension, dyslipidemia, heart failure, ischemic heart disease, and hypersensitivity factor, others

ONIS New Data Co	llection Protocol	Page 17 of 34
Study number: 124	5-0340	Document number: c43224154-01
Proprietary confidential i	nformation © 2024 Boehringer Ingelheim Inter	rnational GmbH or one or more of its affiliated companies
Previous medicati	ant medications and therapies: ons (in the 3 months before star start and end date, reason for u	-
Diet therapy, kine Start and end dat		
		y reason of discontinuation, reason for
Physical measureme Pulse rate, blood p	nts: pressure (systolic / diastolic), bo	ody weight
Laboratory tests (blo Haematology:		emoglobin (Hb), haematocrit (Hct), kocyte fraction (neutrophil count,
Blood chemistry:	SGPT), alkaline phosphatase (γ-GTP), albumin, total biliru total cholesterol (T-CHO), H	glucose, creatinine (CRE), SGOT), alanine transaminase (ALT, (ALP), gamma-glutamyl-transferase bin (T-BIL), blood urea nitrogen (BUN), DL cholesterol (HDL), LDL cholesterol ic acid (UA), ketone, BNP, NT-pro BNP
Urinalysis:		tone, creatinine, Urine Protein-to- ine Albumin-to-Creatinine Ratio (UACR)
Body Mass Inc BMI (kg/m ²)	lex (BMI): = weight(kg) / height ² (m ²)	
	al dysfunction are as follows. lerived from serum creatinine. eGFR ≥90 mL/min/1.73m ² eGFR ≥60 mL/min/1.73m ² an eGFR ≥30 mL/min/1.73m ² an eGFR <30 mL/min/1.73m ²	_
Normal:	derived from urinary albumin a UACR <30 mg/g uria UACR ≥30 mg/g and <3 uria UACR ≥300 mg/g	
UPCR will be Normal:	derived from urinary protein an UPCR <0.15 g/g	nd creatinine.

otocol

Page 18 of 34

Study number: 1245-0340

Document number: c43224154-01

Proprietary confidential information © 2024 Boehringer Ingelheim International GmbH or one or more of its affiliated companies

MicroalbuminuriaUPCR ≥ 0.15 g/g and < 0.50 g/gMacroalbuminuriaUPCR ≥ 0.50 g/g

Enzymatic method (R12-4182): eGFR (mL/min/1.73 m²) = $194 \times \text{Creatinine} (\text{mg/dL})^{-1.094} \times \text{Age}^{-0.287}$ For female, ×0.739 Jaffe rate assay (R09-1573): eGFR (mL/min/1.73 m²) = $175 \times \text{Creatinine} (\text{mg/dL})^{-1.154} \times \text{Age}^{-0.203}$ For female, ×0.742

9.4 DATA SOURCES

Case Report Forms (CRFs) for individual patients will be provided by the sponsor via the EDC system.

In EDC system, two casebooks will be set:

Book 1 includes baseline, 12 weeks and 26 weeks. Book 2 includes 40 weeks and 52 weeks.

The data are to be transmitted immediately after being entered into EDC at 26 weeks (Book 1) and 52 weeks (Book 2) after the start of treatment or at discontinuation. For any adverse events, the data should be immediately entered into EDC and transmitted.

9.5 STUDY SIZE

800 patients (safety analysisset) will be included in the study. 1000 patients will be enrolled to attrition.

The proportion of patients with relevant volume depletion events in the empagliflozin group in the Japanese population of EMPA-KIDNEY trial was 5.1% (15/292). Assuming that proportion is the true proportion of patients that will experience relevant volume depletion events in this PMS study, the precision of the estimate of the proportion of the events relevant volume depletion would be approximately 1.5%, as one-sided width of the 95% confidence interval, if 800 Japanese patients are available as safety analysis population. Possible risk factor associated with the events relevant volume depletion is the concomitant diuretics, and the observed proportion of it was 19.5% (57/292) in the Japanese population of EMPA-KIDNEY trial. Assuming the true proportion of "yes" risk factor in the study is 19.5%, the true proportion of the events relevant volume depletion in the patient population with "yes" risk factor is 5.1%, and the true odds ratio of 2.5 for "yes" risk factors to "no" risk factor, the power to detect differences of the proportion of the events relevant volume depletion between "yes" risk factor and "no" risk factor at a two-sided significance level of 5% is 82% (which is more than 80%), when 800 Japanese patients are included in the PMS study.

ONIS New Data Collection Protocol

Page 19 of 34

Study number: 1245-0340

Document number: c43224154-01

Proprietary confidential information © 2024 Boehringer Ingelheim International GmbH or one or more of its affiliated companies

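### The stated 82% power for the diuretic comparison does not follow from its stated inputs: as written they give about 53%, and no reading supports both justifications for 800 patients

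*Protocol*

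**What the plan says.** Section 9.5 (Study Size) gives two reasons for the number of patients. The base is stated as "800 patients (safety analysisset) will be included in the study".

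- **Precision.** The proportion with volume depletion events was 5.1% (15/292) among Japanese empagliflozin patients in the earlier trial. The section carries this over to the whole surveillance population: "Assuming that proportion is the true proportion of patients that will experience relevant volume depletion events in this PMS study". With 800 patients it gives a one-sided width of about 1.5% for the 95% confidence interval.
- **Power.** Concomitant diuretic use is named as a possible risk factor, with 19.5% (57/292) *yes*. For the *yes* group the section assumes that the event proportion with the "risk factor is 5.1%, and the true odds ratio of 2.5 for" *yes* relative to *no*. At a two-sided 5% level it says that the power "is 82% (which is more than 80%), when 800 Japanese patients are included in the PMS study".

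Section 9.7 (Data Analysis) describes the analyses as descriptive and exploratory, with no formal hypothesis tests.

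**The concern.** Every input to the power figure is stated, so the figure can be checked from the paragraph alone. Two things look wrong.

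First, 5.1% is assigned to the higher-risk group. An odds ratio of 2.5 then pushes the other 644 patients down to about 2%, which leaves few events and makes 82% implausible. Second, 5.1% serves as the overall proportion in the precision argument and as a subgroup proportion in the power argument. With an odds ratio of 2.5 it cannot be both.

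Volume depletion is the focus of the primary outcome (section 9.3.2.1) and of the regulator's request for more safety data (section 7). Diuretic use is the only risk factor that section 9.5 names for it. A reader told that power exceeds 80% could take an unremarkable diuretic comparison as more reassuring than it is.

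**Working it through.** **Inputs, all from section 9.5.** N = 800; 19.5% *yes*, so n₁ = 0.195 × 800 = 156 and n₀ = 644; two-sided α = 0.05; odds ratio 2.5 (*yes* to *no*); a proportion of 5.1%, whose placement is the question.

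**Precision figure.** 1.96 × √(0.051 × 0.949 / 800) = 0.0152. The stated 1.5% is correct for 5.1% overall.

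**Power formula.** Two-proportion z test with pooled variance under the null:

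power = Φ[(|p₁ − p₀| − 1.96 × SE₀) / SE₁], where SE₀ = √(p̄(1 − p̄)(1/n₁ + 1/n₀)), SE₁ = √(p₁(1 − p₁)/n₁ + p₀(1 − p₀)/n₀), and p̄ = 0.195p₁ + 0.805p₀.

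**(a) As written: 5.1% in *yes*.**
- Odds in *yes* = 0.051/0.949 = 0.05374. Dividing by 2.5 gives 0.02150, so p₀ = 2.10%.
- Expected events: 156 × 0.051 ≈ 8.0 and 644 × 0.0210 ≈ 13.6. Overall 2.7%.
- SE₀ = 0.01443, SE₁ = 0.01850, difference 0.02996.
- Power = Φ[(0.02996 − 0.02829)/0.01850] = Φ(0.09) = **53.6%**.

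**(b) 5.1% in *no*.**
- Odds in *yes* = 0.05374 × 2.5 = 0.13435, so p₁ = 11.84%. Overall 6.4%.
- SE₀ = 0.02186, SE₁ = 0.02728, difference 0.06744.
- Power = Φ[(0.06744 − 0.04285)/0.02728] = Φ(0.90) = **81.6%**. This reproduces the stated 82%.
- Half-width at 6.4% overall: 1.96 × √(0.06415 × 0.93585 / 800) = 0.0170, or 1.7 points rather than 1.5.

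**(c) 5.1% overall, as the precision statement assumes.**
- Solving 0.195p₁ + 0.805p₀ = 0.051 with odds ratio 2.5 gives p₁ = 9.51% and p₀ = 4.03%.
- SE₀ = 0.01963, SE₁ = 0.02473, difference 0.05474.
- Power = Φ[(0.05474 − 0.03848)/0.02473] = Φ(0.66) = **74.5%**.

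**Sensitivity to the test used.**

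| Placement of 5.1% | *yes* / *no* | Overall | Pooled z | Exact, chi-square test | Exact, Fisher test |
|---|---|---|---|---|---|
| (a) *yes* group (as written) | 5.1% / 2.1% | 2.7% | 53.6% | 52.6% | 47.8% |
| (b) *no* group | 11.8% / 5.1% | 6.4% | 81.6% | 81.8% | 79.8% |
| (c) overall | 9.5% / 4.0% | 5.1% | 74.5% | 74.3% | 71.5% |

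Other routes from the written inputs do not come near 82% either: a one-sided 5% level gives 63.2% (pooled z) or 64.2% (Wald test of the log odds ratio), 1,000 patients instead of 800 gives 61.1%, equal group sizes give 62.3%, and 2.5 read as a risk ratio gives 55.5%.

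**What 80% power would need.** With the inputs as written, about 1,718 patients. With 800 patients, an odds ratio of about 4.6 under (a) or about 2.7 under (c).

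**The case against.** The strongest reply is that this is a one-word slip. Giving the reference-group proportion plus an odds ratio is the usual way to set up such a calculation, and doing so with 5.1% returns 82% almost exactly. On that view the calculation was sound, one label is wrong, and 53% describes a scenario the sponsor probably never computed. Using an observed overall rate as the reference-group rate is a common planning approximation. The odds ratio of 2.5 has no stated source, so the gap between 74% and 82% lies within planning uncertainty. Finally, no formal test is planned, the main analysis (section 9.7.1) is a proportion with its confidence interval, and the precision argument for 800 holds on its own.

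Much of this stands. The label slip is the likeliest explanation, 53% is the consequence of the text rather than a measure of what the sponsor intended, and the absence of planned tests limits the harm. Any over-reading of a null diuretic comparison is a risk, not something the protocol plans.

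Two parts do not stand. The label and the 82% cannot both be right, and nothing else in the protocol corrects either. Correcting the label also leaves the section with two overall event rates, 5.1% for precision and 6.4% for power. The 15/292 behind the 5.1% counts all Japanese empagliflozin patients in the earlier trial, not only those without diuretics.

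**Conclusion.** The concern holds. On the inputs as written, power is about 53% (52.6% to 53.6% by the chi-square or pooled z test), some 28 to 29 points below the stated 82%. The 82% requires 5.1% in the *no* group, and that contradicts the overall 5.1% used for precision in the same section. With 5.1% overall, and with 19.5% and an odds ratio of 2.5 kept as stated, power is about 74%, so the claim to exceed 80% fails.

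These results assume 800 analysed patients split exactly 156 to 644 and an unadjusted two-group comparison. The consequence is confined to the second justification. The 1.5-point precision is correct, and the study size does not depend on the power figure.

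**What to change.** Rewrite the power sentences in section 9.5 so that both justifications rest on one set of inputs. Either of these would do:

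1. **Preferred.** Take 5.1% as the overall proportion, with 19.5% on diuretics and an odds ratio of 2.5, and show the implied 9.5% versus 4.0%. State power as about 74% (chi-square test, two-sided 5%), or state that 800 patients give 80% power for an odds ratio of about 2.7. Remove the remark that power is above 80%.
2. **If 5.1% was meant for patients without diuretics.** Say so, keep 82%, and restate the precision on the implied overall proportion: 6.4%, half-width about 1.7 points.

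It would help to add that the comparison is exploratory, in line with section 9.7, so that the power figure is not read as backing a formal test.

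The cost is one paragraph. Under the first option the stated power becomes less favourable; under the second the stated precision does. Enrolment, data collection and the main analysis do not change.

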9.6 DATA MANAGEMENT

Patients' data will be gathered by EDC system provided by external vendor below.

	Contract 1	Contract 2
Company Name		
Outsourced work	EDC system setting Patient registration Clinical Data Management	Document management of contract with site

9.7 DATA ANALYSIS

The statistical analysis plan for the study is summarized below. Full details of the statistical analysis will be documented in the Statistical and Epidemiological Analysis Plan (SEAP), which will be finalized before the end of data collection.

This is a real-world, observational, non-interventional study to collect data on patients under routine medical practice on safety, effectiveness and appropriate use of JARDIANCE[®] Tablets treatment. The analyses in this PMS are descriptive and exploratory by nature. No formal hypotheses tests will be made.

All analyses will be performed on the "safety set" that will include all patients who have received treatment of JARDIANCE[®] Tablet at least one time except those who are found to have no observation after registration, invalid registration, or invalid contract with the site.

Subgroup analyses will be performed if sample size allows. Additional information on planned subgroup analyses are provided in the SEAP.

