9.7.3 Safety analysis

The safety analysis will include all patients who registered in the study and receiving the JARDIANCE[®] Tablets treatment at least one time except those who are found to have no observation after enrolment, invalid registration, or invalid contract with the site (see section 9.7). In general, safety analyses will be descriptive, based on BI standards, and focus on AEs related to the JARDIANCE[®] Tablets treatment.

AEs will be coded using the current version of the Medical Dictionary for Drug Regulatory Activities (MedDRA) and will be based on the concept of treatment emergent AEs. To this end, all AEs occurring between the initiation of JARDIANCE[®] Tablets prescribed at baseline visit and 7 days (inclusive) after the last administration will be considered 'treatment emergent'. An AE is considered to be an ADR if either the physician/investigator who has reported the AE or the sponsor assesses its causal relationship as 'related'.

The frequency of ADRs will be tabulated by system organ class and preferred term according to the current MedDRA version. The frequency of SAEs will also be tabulated likewise. The incidence of ADRs stratified based on patient demographics will also be displayed.

No imputation is planned for missing AE data except for missing onset dates which will be handled according to BI standard.

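### Section 9.5 supports 800 patients partly with the power of a two-sided 5% diuretic comparison, while section 9.7 excludes formal tests and the visible analysis text does not name that comparison

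*Protocol*

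**What the plan says.** Protocol section 9.5 sets the target: "800 patients (safety analysisset) will be included in the study", with 1000 enrolled to allow for attrition. It gives two arguments for that number.

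- **Precision.** Taking the 5.1% (15/292) seen with empagliflozin in the Japanese part of the earlier CKD trial, the plan states: "the precision of the estimate of the proportion of the events relevant volume depletion would be approximately 1.5%, as one-sided width". The interval meant is the 95% one.
- **Power.** "Possible risk factor associated with the events relevant volume depletion is the concomitant diuretics", with a prevalence of 19.5% (57/292). Assuming 5.1% in users and an odds ratio of 2.5, "the power to detect differences of the proportion of the events relevant volume depletion" between the two groups at a two-sided 5% level is given as 82%.

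Section 9.7 calls the analyses descriptive and exploratory and adds: "No formal hypotheses tests will be made". It also allows subgroup analyses if the sample size permits and leaves their details to the SEAP. Section 9.7.1 makes the main analysis a count, a proportion and its confidence interval. Section 9.7.3 names one stratification: "The incidence of ADRs stratified based on patient demographics will also be displayed".

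**The concern.** Power at a significance level is a property of a hypothesis test. If no formal test is to be made, the second argument in 9.5 describes an operating characteristic of an analysis that the protocol says will not happen. Deferral to the SEAP does not cure this, because a SEAP that follows 9.7 cannot contain the test.

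The one risk factor named in the sample-size section is also absent from the visible analysis text. Section 9.3.3 lists diuretics nowhere under demographics, and medications have their own heading there, so the stratification in 9.7.3 does not reach diuretic use. Subgroup analyses are made conditional on sample size, although 9.5 uses this very comparison to argue that the sample size is enough.

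At stake is how the study will be read. A regulator or author could take 9.5 as a promise of a tested diuretic effect with 82% power, and a non-significant or untested result would then be hard to interpret. The primary estimate, the overall incidence, is not affected.

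**Working it through.** **Inputs, all from section 9.5:** N = 800; event proportion 5.1% (15/292 = 5.14%); diuretic prevalence 19.5% (57/292); odds ratio 2.5, users against non-users; two-sided alpha 5%; stated power 82%.

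**1. Precision.** Half-width = 1.96 × sqrt(p(1−p)/N) = 1.96 × sqrt(0.051 × 0.949/800) = 0.0152, or 1.52 points. This reproduces the stated value of about 1.5. The analysis that delivers it is in 9.7.1.

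**2. Group sizes.** 0.195 × 800 = 156 users; 800 − 156 = 644 non-users.

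**3. Rates on the inputs as written (5.1% in users).** Odds in users = 0.051/0.949 = 0.0537. Odds in non-users = 0.0537/2.5 = 0.0215. Rate in non-users = 0.0215/1.0215 = 2.1%. Expected events: 156 × 0.051 = 8.0 and 644 × 0.021 = 13.6.

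**4. Power.** Two-sided test of two proportions, pooled variance under the null, 156 v 644 patients:

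| Where the 5.1% is placed | Users | Non-users | Power |
|---|---|---|---|
| Users, as the text says | 5.1% | 2.1% | 53.6% |
| Non-users | 11.8% | 5.1% | 81.6% |
| All patients | 9.5% | 4.0% | 74.5% |

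Exact calculation with the Pearson test gives 52.6%, 81.8% and 74.3% for the three rows. The stated two-sided 82% fits only the second row, which is not what the text says.

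**5. What an estimate would deliver.** Half-width for the difference = 1.96 × sqrt(p1(1−p1)/156 + p2(1−p2)/644).

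- As written: 1.96 × sqrt(0.051 × 0.949/156 + 0.021 × 0.979/644) = 3.6 points, around a difference of 5.1 − 2.1 = 3.0 points. By group, about 3.5 points (users) and 1.1 points (non-users).
- With 5.1% in non-users: 1.96 × sqrt(0.118 × 0.882/156 + 0.051 × 0.949/644) = 5.3 points, around a difference of 11.8 − 5.1 = 6.7 points. By group, about 5.1 and 1.7 points.

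**6. Sections side by side.** Section 9.5 states a significance level and power for users against non-users. Section 9.7 excludes formal tests. Sections 9.7.1 and 9.7.3 specify overall estimation and a demographic stratification. The first two cannot both stand as written. The last two carry out the precision argument but do not name the diuretic comparison.

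**The case against.** The strongest reply is that the size of the study does not depend on the test. Precision comes first in 9.5, reproduces, and matches 9.7.1. An exploratory surveillance study may also quote power as a planning benchmark without promising a confirmatory test. The first part stands: a reader might infer that the diuretic comparison alone sized the study, and the documents do not support that. The second part is only a partial answer, because 9.5 does not call the figure a benchmark, and it states a significance level for a test that 9.7 rules out.

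A reader might also infer that adverse drug reactions will be stratified by demographics and nothing else, so that the study will give no estimate by diuretic use. The documents do not support this either. Section 9.7.3 does not limit stratification to demographics, and 9.7 leaves planned subgroups to the SEAP, which is not at hand. The visible text also passes from 9.7.1 to 9.7.3, so something may have been removed. What can be said is that the visible protocol does not commit to the comparison.

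Finally, because the flow chart (9.2.5) records concomitant medication throughout observation, a reader might infer that patients would be classed by any diuretic use during follow-up, with immortal-time bias and reverse causation. That is a data-collection rule, not an exposure definition. Section 9.3.3 frames its variables as baseline characteristics. No such bias is established; fixing the classification at baseline is only a safeguard.

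**Conclusion.** The point holds as a contradiction between 9.5 and 9.7 on one of two justifications for 800 patients. It does not undermine the number itself, which the 1.52-point precision still supports at 5.1%, and it does not touch the primary estimate.

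Its size lies in what the diuretic comparison can deliver: 156 against 644 patients and, on the inputs as written, about 8 against 14 events and a difference of 3.0 +/- 3.6 points, an interval that includes zero. If the 5.1% was meant for non-users, it is 6.7 +/- 5.3 points. These figures assume that 800 patients are evaluable, that diuretic prevalence is 19.5%, and that the odds ratio is 2.5. That the stated 82% does not follow from the inputs as written (about 54%) is a separate error, but a further reason not to leave the sentence as it stands. The correction should be made; it is one of wording and specification, not of design.

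**What to change.** Make the two sections agree in one of two ways.

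- **(a) Keep the comparison.** Name in 9.7 an exploratory comparison of volume-depletion incidence by diuretic use at first administration (yes/no), reporting the odds ratio and the risk difference with 95% confidence intervals. In 9.5, replace the power sentence with the expected precision, and state which group the 5.1% belongs to. On the inputs as written this is 156 v 644 patients, 5.1% v 2.1%, difference 3.0 +/- 3.6 points.
- **(b) Drop it.** Delete the power sentence and rest 800 on the 1.5-point half-width.

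Wherever diuretic use is analysed, classify it at baseline from the medication start and end dates that 9.3.3 already collects.

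The cost is protocol and SEAP wording and, under (a), one extra table. No new data are needed. The price is a less favourable stated figure than 82% power.

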9.7.1 Main analysis

In this PMS, since the primary outcome is the incidence of ADRs (with a focus on the events relevant to volume depletion), the main analysis is to estimate frequency and proportion (n,%) of patients experiencing events and its corresponding confidence interval (CI). The details are given in section 9.7.3.

ONIS New Data Collection Protocol

Study number: 1245-0340

Page 20 of 34 Document number: c43224154-01

Proprietary confidential information © 2024 Boehringer Ingelheim International GmbH or one or more of its affiliated companies

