4. ABSTRACT

Name of company:				
Boehringer Ingelheim				
Name of finished medicinal product: JARDIANCE [®] Tablets				
Name of active ingre Empagliflozin	edient:			
Protocol date:	Study number:	Version/Revision:	Version/Revision date:	
22 Apr 2024	1245-0340	Version 1.0	Not applicable	
Title of study:		Surveillance on Long Term Use ronic Kidney Disease (CKD) in		
Rationale and background:	In Japan, post-approval execution of Post Marketing Surveillance is requested by the Japanese Pharmaceuticals and Medical Devices Act (J- PMD Act) in order to accumulate safety and effectiveness data for re- examination. Re-examination period is defined by J-PMD Act. Four years after approval of additional indication, results of PMS need to be submitted as a part of re-examination dossier to the Japanese regulatory authority, the Ministry of Health, Labour and Welfare (MHLW). Collected data from PMS will be included in the Japanese periodic safety reports and submitted to MHLW on designated dates until the end of re- examination period.			
Research question and objectives:	Study objective is to investigate the safety and effectiveness of long-term daily use of JARDIANCE [®] Tablets in patients with CKD under real-world use.			
Study design:	Cohort study Non-interventional, single arm study based on newly collected data Patients will be observed for up to 52 weeks after the start of the treatment with JARDIANCE [®] Tablets or until discontinuation of administration.			
Population:	 Inclusion criteria Patients with CKD who are prescribed JARDIANCE[®] Tablets for CKD according to the current Japanese package insert and who provided written informed consent prior to enrolment in this study. Patients who have never been treated with JARDIANCE[®] Tablets (including treatment for T2DM and/or CHF) before enrolment. Exclusion criteria None 			

ONIS New Data Collection Protocol

Page 9 of 34

Study number: 1245-0340

Document number: c43224154-01

Variables:	These outcomes are reported over the observational period.					
	Outcomes:					
	Primary outcome:					
	- Incidence of adverse drug reactions (focus on the safety specification on Japan Risk Management Plan (J-RMP): The events relevant volume depletion)					

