9.2.3 Study visits

The patients will be observed for up to 52 weeks after the start of the treatment with JARDIANCE[®] Tablets or discontinuation of administration.

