9.3 VARIABLES

9.3.1 Exposures

Exposure to JARDIANCE[®] Tablets is estimated as time from the day JARDIANCE[®] Tablets is initiated until the day the drug is last administrated on a patient-level (or the final contact with the patient during the regular observation period).

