9.3.2 Outcomes

These outcomes are reported over the observational period.

ONIS New Data Collection Protocol

Page 16 of 34 Document number: c43224154-01

Study number: 1245-0340

Proprietary confidential information © 2024 Boehringer Ingelheim International GmbH or one or more of its affiliated companies

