9.3.2.1 Primary outcomes

The primary outcome of this study is the incidence of ADRs (focus on the events relevant volume depletion).

The ADR definition and reporting is described in section 11.

There is no primary outcome for effectiveness as the primary objective of a PMS is evaluating safety.

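### The main analysis gives only a crude percentage with ADRs although time on treatment varies; add a rate and a 52-week cumulative incidence beside it

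*Protocol*

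**What the plan says.** All references are to the protocol.

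- **Estimator.** Section 9.7.1: "the main analysis is to estimate frequency and proportion (n,%) of patients experiencing events and its corresponding confidence interval (CI". It refers to section 9.7.3 for details, and that section adds frequency tables by MedDRA term and ADR incidence by patient characteristics.
- **Outcome.** Section 9.3.2.1: "The primary outcome of this study is the incidence of ADRs (focus on the events relevant volume depletion". Section 9.3.2 gives the period: "These outcomes are reported over the observational period".
- **Length of observation.** Section 9.2.3: "The patients will be observed for up to 52 weeks after the start of the treatment with JARDIANCE[®] Tablets or discontinuation of administration". The abstract makes the end point explicit: "or until discontinuation of administration".
- **Counting window.** Section 9.7.3 runs from first dose to "7 days (inclusive) after the last administration will be considered 'treatment emergent".
- **Denominator.** Sections 9.7 and 9.7.3: everyone treated at least once, except patients with no observation after registration, an invalid registration or an invalid site contract.
- **Exposure.** Section 9.3.1 defines it for each patient, from first dose "until the day the drug is last administrated on a patient-level" (or final contact). Neither 9.7.1 nor 9.7.3 uses it.

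**The concern.** Follow-up is unequal by design, and the named estimator ignores this. A patient who stops after two weeks without an event enters the denominator in full, as if event-free over the whole period. The percentage therefore mixes two things: how often reactions occur while patients take the drug, and how long they take it. For the same hazard on treatment, a cohort that stops sooner shows a lower percentage.

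This matters because the stated objective is the safety of long-term daily use. A reader of the final report will naturally take the headline figure as roughly a one-year risk. The ADR incidences by patient characteristics in section 9.7.3 have the same weakness: two strata with equal hazards but different time on drug would show different percentages.

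**Working it through.** **Inputs from the protocol.** Planning proportion 5.1% (15/292) and safety set n = 800 (section 9.5); observation limit 52 weeks (section 9.2.3); 7-day window after the last dose (section 9.7.3).

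**Input assumed.** The share d of patients stopping by week 52. The protocol gives none. The 1000 enrolled for 800 analysed in section 9.5 concerns loss from the safety set, not stopping of treatment. I use d = 10% to 40%.

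**Step 1: the protocol's own figure.** Half-width of the 95% CI = 1.96 × √(0.051 × 0.949 / 800) = 0.0152, or 1.5 percentage points. This agrees with section 9.5.

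**Step 2: constant hazards.** Take a true 52-week on-treatment risk of 5.1%, with stopping unrelated to the event. With time in units of 52 weeks:

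- event hazard h = −ln(0.949) = 0.0523
- stopping hazard g = −ln(1 − d)
- crude proportion = h/(h + g) × [1 − exp(−(h + g))]
- mean time at risk = [1 − exp(−(h + g))]/(h + g)

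Example for d = 20%: g = 0.2231 and h + g = 0.2755. Then 1 − 0.949 × 0.8 = 0.2408, and the crude proportion is 0.0523/0.2755 × 0.2408 = 0.0458.

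| Stopping by week 52 | Crude % | Crude % with 7-day window | Shortfall against 5.1% (no window) | Mean time at risk |
|---|---|---|---|---|
| 10% | 4.84 | 4.85 | 5% | 0.925 |
| 20% | 4.58 | 4.60 | 10% | 0.874 |
| 30% | 4.30 | 4.33 | 16% | 0.821 |
| 40% | 4.00 | 4.04 | 22% | 0.765 |

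Dividing the crude proportion by mean time at risk gives 5.23 first events per 100 patient-years in every row (for example 0.0484/0.925). The rate does not move with d; the percentage does.

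**Step 3: other timings** (same 5.1% risk, 7-day window ignored).

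| Stopping | All events in first 12 weeks | All stopping in first 12 weeks |
|---|---|---|
| 10% | 5.04% | 4.65% |
| 20% | 4.97% | 4.20% |
| 30% | 4.90% | 3.74% |
| 40% | 4.81% | 3.28% |

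The shortfall is at most 0.3 points if events are early, and 0.5 to 1.8 points if stopping is early.

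**Step 4: does the confidence interval absorb it?** Under step 2, the shortfall is 0.3 to 1.1 points, inside the 1.5-point half-width. But the interval is centred on the wrong value if it is read as a 52-week risk. An exact binomial 95% CI with n = 800 would contain 5.1% about 95%, 92%, 85% and 73% of the time at 10%, 20%, 30% and 40% stopping. The loss is negligible at 10% and clear at 30% or more.

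**The case against.** Four arguments can be made for the plan.

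1. **No 52-week risk is named as the target.** Outcomes cover the observational period. The share of patients with a reaction while on drug in routine use is a coherent descriptive quantity, and early stopping is part of that use. This stands: n/% is not wrong for what it literally measures. It becomes too low only when read as risk over 52 weeks of treatment.

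2. **The SEAP may add a rate or a curve.** Section 9.7 leaves full details to it, and the text available jumps from 9.7.1 to 9.7.3. So it cannot be said that no such analysis will be done. But the main estimator is not left open: section 9.7.1 names it.

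3. **The bias may be small.** With low discontinuation or early events it is. Nothing in the protocol allows a firm figure.

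4. **A curve censored at stopping has its own weakness.** It assumes that patients who stop have the same later event risk as those who continue. Poor tolerability may drive stopping, which would break that assumption. This stands, and it is a good reason not to replace n/%.

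A reader might also infer that the result cannot be compared with the earlier trial's 5.1%, and that this is an error in the plan. The protocol does not support that. The 5.1% is background in section 7 and a planning assumption in section 9.5. No comparison with it is planned, and section 9.7 says that no formal hypothesis tests will be made. It is also a crude proportion itself. If the result is nevertheless set beside it, two cautions apply. The follow-up behind 15/292 is not stated. Section 9.5 describes events with no causality condition, whereas this study counts ADRs.

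**Conclusion.** The concern holds as a cheap improvement, not as an error that invalidates the main analysis. The crude percentage depends on time on treatment and can understate 52-week on-treatment risk when event-free patients stop early. That it will do so materially is not shown.

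Under a true 52-week risk of 5.1%, constant hazards and 10% to 40% stopping unrelated to the event, the expected crude figure is about 4.8% to 4.0%. All of these conditions are assumptions, and the timing of events and of stopping moves the result in both directions.

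**What to change.** In sections 9.7.1 and 9.7.3, keep n/% with its CI, described as the proportion with an ADR during observed treatment. For volume-depletion events add:

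- the first-event rate per 100 patient-years with 95% CI;
- the 52-week cumulative incidence with 95% CI (Aalen-Johansen), with death as a competing event and censoring at the earlier of last dose plus 7 days and week 52;
- the distribution of follow-up time.

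State that the cumulative incidence assumes stopping to be unrelated to event risk.

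No new data are needed: the flow chart in section 9.2.5 records administration status and adverse events throughout, and section 9.7.3 already provides for missing onset dates. The cost is a few sentences, one more table, and an assumption that readers must be told about.
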